2.0 Research Reference Numbers

 IRAS Number:
 169165

 EudraCT Number:
 2015-000301-40

ISRCTN Number / Clinical trials.gov N/A Number:

5.0 Trial Summary

Full title	A randomised, blinded placebo-controlled phase 2a study to evaluate the safety and efficacy of Artesunate treatment in severely injured trauma patients with traumatic haemorrhage.
Short title and/or Acronym	TOP-ART
Trial Design Methodology	Randomised, blinded placebo-controlled, parallel group study.
Phase of the Trial	Phase 2a
Study Duration	27-months.
Study setting	Single-site NHS Major Trauma Centre
Investigational Medicinal Product(s) and Treatment Groups	 IMP: Artesunate provided as a white crystalline powder in a glass vial containing 110mg, supplied with a second glass vial of reconstitution diluent which is a sterile phosphate buffer comprised of a mixture of sodium phosphate monobasic monohydrate, sodium phosphate dibasic anhydrous and water for injection to achieve a 0.3 M solution with a pH of 8.0 (7.9-8.1). Matching placebo will comprise of the same, buffered diluent drawn up to the volume that would be necessary to reconstitute active IMP according to the subjects' weight. The sterile phosphate buffer is provided in a glass vial and is comprised of a mixture of sodium phosphate monobasic monohydrate, sodium phosphate dibasic anhydrous and water for injection to achieve a 0.3 M solution with a pH of 8.0 (7.9-8.1). Treatment group 1 (low dose intervention group): Subjects will be dosed at 2.4 mg/kg. Treatment Group 2 (high dose intervention group): Subjects will be dosed at 4.8 mg/kg. Control Group: Subjects will be receiving placebo at the same dose as treatment groups 1 or 2 respectively
Medical condition or disease under	Trauma haemorrhage
Planned Sample Size	105
(Maximum) Treatment duration	1-2 minutes (time taken to administer bolus injection of IMP or comparator)
Follow up duration	90 Days
End of Trial definition	Point at which all surviving Subjects have completed 90-day mortality check.

8.0 List of Abbreviations / Glossary of Terms

AE	Adverse Event
ACCU	Adult Critical Care Unit
ANOVA	Analysis of Variance
AR	Adverse Reaction
ВНТ	Barts Health NHS Trust
CI	Chief Investigator
CIOMS	Council for International Organisations of Medical Sciences
CONSORT	CONsolidated Standards of Reporting Trials
СРАР	Continuous Positive Airway Pressure
CRF	Case Report Form
CRO	Contract Research Organisation
CTCOFR	Composite Time to Complete Organ Failure Resolution
СТІМР	Clinical Trial of Investigational Medicinal Product
DHA	Dihydroartemesinin
DMC	Data Monitoring Committee
EC	European Commission
eGFR	Estimated Glomerular Filtration Rate
EU	European Union
EUCTD	European Clinical Trials Directive
EudraCT	European Union Drug Regulating Authorities Clinical Trials
eNOS	Endothelial Nitric Oxide Synthase
FiO2	Fraction of inspired Oxygen
GCP	Good Clinical Practice
GCS	Glasgow Coma Score
GMP	Good Manufacturing Practice
GP	General Practitioner
GSK-3β	Glycogen Synthase Kinase-3β
hCG	Human Chorionic Gonadotrophin
НТА	Human Tissue Act
IB	Investigator Brochure
ICF	Informed Consent Form
ICH	International Conference on Harmonisation of Technical Requirements

	for Registration of Pharmaceuticals for Human Use
IgE	Immunoglobulin E
IMP	Investigational Medicinal Product
INR	International Normalised Ratio
ІТТ	Intention To Treat
ISRCTN	International Standard Randomised Controlled Trial Number
JRMO	Joint Research Management Office
LR	Legal Representative
LC-MS/MS	Liquid Chromatography-Mass Spectrometry
МА	Marketing Authorisation
MedDRA	Medical Dictionary for Regulatory Activities
MHRA	Medicines and Healthcare products Regulatory Agency
Main REC	Main Research Ethics Committee
MOF	Multiple Organ Failure
MORU	Mahidol Oxford Research Unit
n	number
NF-⊡B	Nuclear Factor-ĸB
NHS R&D	National Health Service Research & Development
PaO2	Partial pressure of arterial Oxygenation
PEEP	Positive End Expiratory Pressure
PI	Principle Investigator
рКа	-log ₁₀ (Ka)
	Ka represents the acid dissociation constant
PK/PD	Pharmacokinetic/Pharmacodynamic
РР	Per Protocol
РТ	Preferred Term
QMUL	Queen Mary University of London
RGF	Research Gorvernance Framework
RIFLE	Risk, Injury, Failure, Loss of function, Endstage renal failure
RRT	Renal Replacement Therapy
Subject	An individual who takes part in a clinical trial
REC	Research Ethics Committee
SAE	Serious Adverse Event
SAR	Serious Adverse Reaction

SmPC	Summary of Product Characteristics
SOC	System Organ Class
SOFA	Sequential Organ Failure Assessment
SOP	Standard Operating Procedure
SUSAR	Suspected Unexpected Serious Adverse Reaction
TMF	Trial Management File
TMG	Trial Management Group
TSC	Trial Steering Committee
WHO	World Health Organisation
WWARN	World-Wide Antimalarial Resistance Network

9.0 Introduction

9.1 Background

Multiple organ failure is common (30%) in the severely injured population and, if not fatal, results in worse outcomes such as prolonged critical care and hospital stays, and poor long-term quality of life. Development of multiple organ failure occurs early (within two days of admission) and correlates with an increase in nosocomial infections and if it persists, mortality (Minei *et al.* 2012). This figure rises rapidly as the degree of blood loss and shock intensifies. Patients requiring at least four units of red cell transfusions have longer critical care (9 vs. 5 days) and hospital stays (25 vs. 15 days). They also have a higher mortality (35% vs. 6%). Even modest improvements in these figures would have a significant improvement on patient experience, quality of life and the costs of healthcare.

Currently there are no specific treatments for organ failure. A therapeutic agent that reduces the incidence and severity of multiple organ failure could have a major global impact on the patient outcomes and resource utilisation.

The World Health Organisation (WHO) recommends intravenous Artesunate (a semi-synthetic artemisinin derived from the plant *Artemisia annua*) as the treatment of choice for severe malaria (WHO, 2010). Artesunate has very few adverse effects and the recommended intravenous bolus dose in adults/children with malaria is 2.4 mg/kg. Artesunate has been used by thousands of patients with malaria without important adverse effects (Sinclair *et al.* 2012). In man, Artesunate has a half-life of less than 30 mins and its active metabolite dihydroartemesinin (DHA) of less than 3 hrs. According to the WHO, the dose of Artesunate does not have to be adjusted in patients with renal failure or liver dysfunction.

In the first phase of the study, the dose of Artesunate (single bolus intravenous injection) proposed for administration to patients with trauma-haemorrhage is identical to the dose currently recommended by the WHO for the treatment of malaria (2.4 mg/kg), although in malaria Artesunate is repeatedly administered (every 12hrs), whilst in this study only one bolus dose will be injected. Thus, no significant adverse effects with Artesunate in patients with trauma-haemorrhage are expected. Provided the interim analysis demonstrates no safety concerns, the trial will proceed with the higher dose of Artesunate (4.8 mg/kg)—see also Section 9.2 for further safety data.

Pre-Clinical Data

We have discovered that the intravenous injection of small doses of Artesunate (1-10 mg/kg) upon resuscitation after severe haemorrhage (rat) reduces the multiple organ failure after trauma-haemorrhage by enhancing the resistance of organs against injury by a) activating well-known cell-survival pathways, and b) reducing excessive inflammation.

We have discovered preclinical (rat) efficacy of low doses of Artesunate (up to 10 mg/kg) in traumahaemorrhage i.e. removal of approximately 40% of blood volume for 90 mins followed by resuscitation for 4 hrs resulting in multiple organ (kidney, lung, liver) failure. Intravenous injection upon resuscitation (after 90 mins of haemorrhage) of low dose Artesunate (1-10 mg/kg) attenuates the multiple organ failure (renal dysfunction, liver injury, neuromuscular injury) caused by severe haemorrhage by 50-90% (Fig. 1) by activating well-known survival pathways or by inhibiting proinflammatory pathways (Fig 2).

The most effective dose was 3 mg/kg, and a higher dose (10 mg/kg) offered no further significant benefit. Using the same protocol, we have then evaluated the effects of 2.4 or 4.8 mg/kg

intravenous artesunate in rats with severe haemorrhagic shock. This study confirmed that Artesunate caused a dose-related reduction in multiple organ injury/dysfunction (Fig 3).

When given after a prolonged (90 min) period of severe haemorrhage (leading to a fall in mean arterial blood pressure to 35 mmHg), Artesunate (2.4 or 4.8 mg/kg i.v.) attenuates the renal (glomerular) dysfunction, liver injury and neuromuscular injury by 50 to 90%. In the liver of rats with haemorrhagic shock, Artesunate also activates a well-known survival pathway resulting in activation of Akt (pro-survival), activation of eNOS (vasodilator and pro-survival), inhibition of GSK-32 and NF-2B (anti-inflammatory), which contribute to or account for the observed beneficial effects of Artesunate.

Figure 1: Effect of Artesunate on (A) mean arterial pressure monitored throughout haemorrhage and resuscitation, (B, C) renal dysfunction; serum creatinine levels and creatinine clearance, (D, E) liver injury; serum aspartate aminotransferase (AST) and alanine aminotransferase (ALT) levels, and (F) neuromuscular injury; serum creatine kinase levels were measured subsequent to sham-operation (Sham + Vehicle, n=10; Sham + Artesunate 10 mg/kg, n=10) or haemorrhagic shock (HS + Vehicle, n=10; HS + Artesunate [1 mg/kg i.v.], n=10; HS + Artesunate [3 mg/kg i.v.], n=10); HS + Artesunate [10 mg/kg i.v.], n=10. Data represent mean ± SEM for n observations, **P*<0.05 *vs*. Sham + Vehicle, #*P*<0.05 *vs*. HS + Vehicle.

Figure 2: Effect of Artesunate on the phosphorylation of (A) Ser⁴⁷³ on Akt in the liver, (B) Ser¹¹⁷⁷ on eNOS in the liver, (C) Ser⁹ on GSK-3 β in the liver, and (D) nuclear translocation of p65 (NF- κ B activation) subsequent to subjected to sham-operation (Sham + Vehicle, n=3) or haemorrhagic shock (HS + Vehicle, n=10); and HS + Artesunate 10 mg/kg, n=3. Data represent mean ± SEM for n observations, **P*<0.05 *vs.* Sham + 10% DMSO, #*P*<0.05 *vs.* HS + 10% DMSO.

Figure 3: Effect of Artesunate on (A) mean arterial pressure monitored throughout haemorrhage and resuscitation, (B) global organ perfusion; lactate levels, (C, D) renal dysfunction; serum creatinine levels and creatinine clearance, (E, F) liver injury; serum aspartate aminotransferase (AST) and alanine aminotransferase (ALT) levels, (G) pancreas injury; amylase levels, and (H) neuromuscular injury; serum creatine kinase levels were measured subsequent to sham-operation (Sham + Vehicle, n=7) or haemorrhagic shock (HS +)

Clinical Data

Following an in-depth review of the literature, there are no human studies demonstrating use of Artesunate as a treatment for reducing multiple organ failure resulting from severe haemorrhage and injury. However, due to widespread use of Artesunate for the treatment of severe malaria, it has been available outside of the UK (and 'off-licence' inside the UK) in various non-GMP formulations (parenteral, oral, and rectal suppository) for a number of years. Therefore, there is a large volume of published information about clinical experiences with the drug, including in critically ill malaria patients. Collectively these studies have involved thousands of subjects. Several peer reviews have summarised various aspects of Artesunate trials, and have found Artesunate to be safe and well-tolerated (Riberio & Olliaro 1998, McIntosh & Olliaro 2000, Jones *et al.* 2007, Nosten & White 2007, Hess *et al.* 2010, Sinclair *et. al* 2012).

In a review of 188 (published and unpublished) trials, including 9241 subjects treated with Artesunate for malaria, Riberio & Olliaro (1998) found no serious adverse events or severe significant toxicity in a safety analysis of adverse events. In this review the most commonly reported adverse experiences were gastrointestinal symptoms. Occasional neutropenia (1.3%) reticulocytopenia (0.6%) and elevated liver enzymes (0.9%) were reported, and occasional instances of bradycardia/prolonged QT intervals (1.1%). Reports of neuropsychiatric disorders were reported in 4 patients on however they were all on con-current mefloquine.

McIntosh & Olliaro (2000) examined 41 trials of Artesunate in over 5000 patients and concluded that there was no evidence to suggest artemesinin drugs were more harmful than standard treatment for uncomplicated malaria. Similarly, Sinclair et al. (2012) examined 8 trials of Artesunate in severe malaria involving 1664 adults and 5765 children and reported no evidence of adverse effects of Artesunate, except for transiently worse neurological sequale in children.

Although artemisinins are recognized as a family of exceptionally safe drugs there have been four cases of IgE-mediated anaphylactic reactions to oral and intravenous Artesunate (Leonardi *et al.* 2001, Mohapatra *et al.* 2009, Dube *et al.* 2012). These allergic reactions to artemisinins are considerably rare.

With respect to pregnancy, there are Cochrane database reviews of uncomplicated malaria treatment in pregnant women that discuss Artesunate (Orton & Garner 2005, Orton & Omari 2008). The current guidance suggests Artesunate may be given in the second and third trimesters for treatment of malaria, however due to insufficient evidence, it is not currently recommended for use in the first trimester unless benefits are considered to outweigh the risks (WHO, 2010).

With regards to the increased dose (4.8 mg/kg) we similarly do not expect significant adverse effect based on safety studies demonstrating that Artesunate can be safely administered up to doses of 8 mg/kg; Healthy volunteer Phase 1 studies have shown that single and multiple doses of intravenous Artesunate at the highest dose tested (8 mg/kg) were well tolerated with no serious side effects observed, and showed no dose-dependant increase in any adverse events, apart from a dose-related decrease in reticulocyte counts four days after dosing (Li *et al.* 2009, Miller *et al.* 2012).

9.2 Assessment and management of risk

Artesunate has been extensively used in the treatment of both child and adult malaria including use in critically ill patients. They are very well tolerated, with a well-documented safety profile (see

previous section). As patients will receive all other clinically indicated treatments, there is no risk of ineffective therapy by administration of the trial treatment.

Whilst there is a risk of adverse events occurring as a result of oral or intravenous Artesunate, including gastrointestinal symptoms, neutropenia, reticulocytopenia, liver enzyme disturbance, bradycardia and prolonged QT intervals (Riberio & Olliaro 1998), these risks are low (all occurring in under 1.5% of recipients) and unlikely to result in significant detriment to the subject particularly in light of the serious nature of their injuries. Moreover, anaphylactic reactions to Artesunate are extremely rare.

The potential benefits of Artesunate in reducing multiple organ failure outweigh the risk of adverse events associated with the medication. Artesunate will be administered as an intravenous preparation due to the critical illness of the subjects enrolled that will preclude oral administration. Intravenous Artesunate has been more widely studied within the literature compared to intramuscular Artesunate (Jones *et al.* 2007) and is therefore the preferred route of administration in this trial.

This trial is categorised as: Phase 2a

9.3 Rationale for study design

This study aims to investigate whether administration of a single intravenous bolus dose of Artesunate reduces multiple organ failure in severely injured patients with trauma haemorrhage. The rationale for the study include:

- 1. Pre-clinical data provide both clinical and mechanistic evidence of the potential benefit of Artesunate in reducing multiple organ failure.
- 2. There are currently no other specific therapeutic agents that are proven to effectively attenuate multiple organ failure and its detrimental consequences in human studies (Lord et al., 2014)
- 3. Artesunate has a well-documented favourable safety profile, including in other critical illnesses.

The patient will receive the usual standard of care regardless of whether or not they receive Artesunate. With regards to dosage, 2.4mg/kg as a bolus is the recommended treatment does for malaria (a bolus which is repeated 12 hours later). There is published safety data for Artesunate using intravenous boluses up to 8mg/kg (Li *et al.* 2009, Miller *et al.* 2012).

In our study, due to the dose-dependent benefit seen in the pre-clinical data, we wish to determine whether an increased dose of 4.8mg/kg Artesunate is more efficacious than 2.4mg/kg in reducing multiple organ failure following major haemorrhage in trauma. We do not expect a significant increase in serious adverse events in relation to this increased dose, although this will be closely monitored.

A placebo is justified in this trial to reduce effects of potential investigator bias when collecting follow-up data (including on organ failure) and potential bias arising from differential treatment by clinicians on account of knowing the patient's enrolment in the trial.

Please see section 9.2 for further assessment of the risks and benefits of the study.

10.0 Trial Flowchart

11.0 Trial Objectives and Design

11.1 Primary Objective/s

The aim of this study is to determine whether treatment with Artesunate compared with placebo improves the outcome in severely injured trauma subjects with haemorrhage.

11.2 Secondary Objective/s

The secondary objectives of the study are, to determine the effects of Artesunate on organ failure, lung injury, kidney injury, infection, ventilator requirements, hospital stay, critical care stay and mortality.

The safety objective is to evaluate the safety of Artesunate in the treatment of severely injured trauma subjects.

11.3 Endpoints

11.3.1 Primary Endpoint

The primary efficacy endpoint is reduction in SOFA score at 48 hours for Artesunate treatment arm versus placebo.

11.3.2 Secondary Endpoint

The secondary endpoints are:

- Maximum SOFA score: Maximum SOFA score over 7 days.
- Mean SOFA Score (Days 2-5).
- Prolonged organ failure: Defined as SOFA>5 on Day 7.
- Days on organ support: As per the CTCOFR score (Nadel *et al.*, 2007).
- Incidence of acute lung injury: As per Berlin definition (ARDS Task Force, 2012).
- Incidence of acute kidney injury: As per the RIFLE score (Bellomo *et al.*, 2004).
- Incidence of infection: As per definitions of infection by (Cole *et al.*, 2014).
- Number of ventilation free days.
- Total length of hospital stay.
- Total length of critical care stay.
- Mortality (discharge, 28 day and 90 day).
- Alive and free of multiple organ failure (defined as SOFA <=>) at 48 hours.

The safety endpoint is the serious adverse event rate in the first 28 days.

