Please see Appendix 2 for a full description of the outcome measures that will be recorded, including: SOFA Score, Renal injury (RIFLE Score), Lung Injury (ARDS Score), Infection rate, and days of organ failure (CTCOFR score).

Ventilator free days will be calculated by the subtracting the number of days spent on mechanical ventilation from 28.

Renal replacement therapy days will be calculated as the number of days spent on haemodialysis or haemofiltration.

Vasopressor days will be calculated as the number of days spent on ionotropic drugs, including for instance noradrenaline, dobutamine, vasopressin.

Length of stay will be recorded in days, for the total number spent in ACCU and in Hospital.

Mortality will be recorded at 28 days, discharge and 90 days.

At 48 hours it will be recorded whether the patient was alive and free of multiple organ failure (defined as SOFA≤5).

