13.9 Withdrawal criteria

Every reasonable effort will be made to maintain protocol compliance and to retain patient participation in the study consistent with the provisions of informed consent and good clinical practice. The following are potential reasons why a patient may be withdrawn from the study:

- 1. Withdrawal of consent: the patient, the patient's authorised representative, independent physician, or designated individual who had provided initial consent to enter the study may withdraw consent at any time throughout the duration of the trial, without prejudice to future medical care and treatment.
- 2. Retrospective exclusion: If a patient is deemed to not meet one or more of the inclusion/exclusion criteria in retrospect they will be withdrawn from the study.
- 3. Major protocol deviation from the study design by the subject, observed or suspected by the investigator.
- 4. Adverse event.
- 5. Administrative: the sponsor or monitoring committees decide to terminate or discontinue the study.
- 6. The subject's health would be jeopardised by continued participation and is withdrawn at the discretion of the investigator.

Data Collection And Follow-Up For Withdrawn Subjects

If a patient is withdrawn from the study before receiving IMP but after randomisation, any ongoing SAE experienced by the patient, which are not injury- or standard-treatment related, will be followed to resolution but no other safety or efficacy assessments will be conducted.

Patients who withdraw from the study after receiving IMP should be followed for safety by conducting safety assessments through to the end of day 28. If a patient who withdraws has develops an SAE during the monitoring period, every effort must be made to follow such events until satisfactory resolution is obtained or until further follow-up is no longer warranted.

Any samples obtained from withdrawn participants will be discarded in accordance with the Bart's Health NHS Trust standard procedures.

Replacement Of Subjects

Subjects who do not complete the primary outcome end-point at 48-hours (e.g. due to death or discharge) will be replaced. Subjects who withdraw from the study at any time point will also be replaced. Withdrawn participants will not be permitted to re-enter the study.

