19.6 Secondary outcome analysis

Secondary Outcome Analysis

The secondary endpoints that are continuous variables include: maximum SOFA score, mean SOFA Score (Days 2-5), number of days on organ support, number of ventilation-free days, number of days

in hospital, and number of days in critical care. Placebo and treatment groups will be analysed using appropriate standard tests of two-group comparison depending on data normality.

The secondary endpoints that are catagorical variables include: incidence of acute kidney injury as per the RIFLE classification. Secondary endpoints that are nominal variables include: incidence of prolonged organ failure, incidence of acute lung injury, incidence of infection, mortality rate (28-day, 90-day and discharge), and 'alive and free of multiple organ failure' at 48 hours. Placebo and treatment groups will be analysed using appropriate standard tests of two-group comparison.

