19.11 Procedure(s) to account for missing or spurious data

The study team will follow participants daily in order to maximise capture of follow-up data. Missing outcome data will be imputed where appropriate. Reasons for missing data will be recorded on the CRF during data capture where possible (e.g. observation not performed, sample not taken).

19.12 Other statistical considerations.

Any deviations from the original statistical plan will be reported in the clinical study report with reasons for doing so. Participants who withdraw from the study will be replaced. Evaluable patients are defined as those who meet study inclusion and exclusion criteria, provide consent for participation, are randomised to either treatment or comparator group and treated according to protocol, and reach the primary endpoint (SOFA score at 48 hours). Evaluable patients will analysed in the 'per protocol' analysis for comparison against the intention-to-treat analysis.

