APPENDIX 2: SCORING SYSTEMS AND DEFINITIONS

PARAMETER	SCORE BREAKDOWN				
	0	1	2	3	4
PaO2/FiO2 ratio	>53.3	≤53.3	≤40	≤26.7	≤13.3
Platelets	≥150	<150	<100	<50	<20
Bilirubin	<20	20-32	33-101	102-204	>204
CVS	MAP	MAP<70	Dopamine ≤5	Dopamine >5 or	Dopamine >15 or
	≥70		or any dose	adrenaline ≤0.1 or	adrenaline >0.1 or
			dobutamine	noradrenaline	noradrenaline >0.1
				≤0.1 mcg/kg/min	mcg/kg/min
GCS	15	13-14	10-12	6-9	<6
Creatinine	≤109	110-170	171-299	300-440 or urine	>440 or urine
				<500ml/day	<200ml/day

1. SOFA Score Parameters (Vincent et al. 1998)

2. CTCOFR Scoring parameters (Nadel et al. 2007)

PARAMETER	DESCRIPTION	
Last day vasoactive agent	dobutamine <5 μg/kg/min or cessation of	
	adrenaline/noradrenaline/phenylephedrine or other	
	vasoactive agent	
Last day mechanical ventilation	IPPV, CPAP, Bimodal	
Last day renal replacement therapy:	peritoneal dialysis, haemodialysis, ultrafiltration,	
	haemofiltration	
For each parameter score 1 point per day up to 14 days		
Total CTCOFR Score if composite >14 days = 15 points		
Total CTCOFR Score if death during study (28 days) = 16 points.		

3. RIFLE Score Parameters (Bellomo et al. 2004)

	EGFR/SERUM CREATININE (Cr)	URINE OUTPUT
Risk	Cr x 1.5 or; eGFR decrease by >25% <0.5ml/kg/h for	
Injury	Cr x 2 or; eGFR decrease by >50%	<0.5ml/kg/h for 12 hours
Failure	Cr x 3 or; GFR decrease by >75% or; If baseline Cr	<0.3ml/kg/h for 24 hours
	>353.6 µmol/L, increase of 44 µmol/L	or; anuria for 12 hours
Loss of function	Complete loss of function >4 weeks	
End-stage kidney	Complete loss of function > 3 months	
disease		

4. Acute Lung Injury Definitions (ARDS Task Force, 2012)

THE BERLIN DEFINITION OF ACUTE RESPIRATORY DISTRESS SYNDROME		
TIming	<1 week of a known clinical insult or new or worsening respiratory symptoms	
Chest Imaging ^a	Bilateral opacities not fully explained by effusions, lobar/lung collapse,	
	nodules	
Origin of	Respiratory failure not fully explained by cardiac failure or fluid overload.	
Oedema	Need objective assessment (e.g. echocardiography) if no risk factor present.	
Oxygenation:		
Mild	200mmHg <pao2 cpapb ≥5 cmH2O</pao2>	
Mod	100mmHg <pao2 cmh2o<="" fio2="" peep="" td="" with="" ≤200mmhg="" ≥5=""></pao2>	
Severe	PaO2/FiO2 ≤100mmHg with PEEP ≥5 cmH2O	
a: Chest radiograph or Computed Tomography scan		
b: This may be delivered non-invasively in the mild acute respiratory distress syndrome		

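### Prolonged organ failure on Day 7 has no rule for patients who die before Day 7, so the endpoint can move against a drug that prevents early deaths

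*Protocol*

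**What the plan says.** Section 11.3.2 of the protocol lists "Prolonged organ failure: Defined as SOFA>5 on Day 7" among the secondary endpoints. Section 19.6 treats it as binary: "Secondary endpoints that are nominal variables include: incidence of prolonged organ failure", compared between placebo and treatment by standard two-group tests. The SOFA table in Appendix 2 scores six physiological items from 0 to 4 and has no entry for a patient who has died.

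Two other endpoints do deal with death. For days on organ support, Appendix 2 states "Total CTCOFR Score if death during study (28 days) = 16 points", the worst value on that scale. For the early endpoint, section 13.8.3 states "At 48 hours it will be recorded whether the patient was alive and free of multiple organ failure", so a patient who has died by then cannot count as a good outcome.

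Two further provisions bear on the point. Section 13.9 states "Subjects who do not complete the primary outcome end-point at 48-hours (e.g. due to death or discharge) will be replaced", and 19.12 limits evaluable (per-protocol) patients to those who reach the 48-hour SOFA. Section 19.10 keeps every randomised patient in the ITT population. On missing data, 19.11 says "Missing outcome data will be imputed where appropriate", with no method and no mention of death.

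**The concern.** Only a living patient can have a SOFA score on Day 7. A patient who dies on Day 3 of multiple organ failure has had the outcome the drug is meant to prevent, yet on the wording is not a case, or is left out.

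Section 9.1 links persisting multiple organ failure to mortality, so death before Day 7 is not independent of what the endpoint measures. A drug that keeps such patients alive, some of them still in organ failure on Day 7, adds cases to its own arm. A drug that hastened death would remove them. Either way the endpoint can point in the wrong direction. It is one of the organ-failure endpoints in 11.5, in a trial that 19.1 says should inform whether a phase 2b study is justified.

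**Working it through.** The plan gives no figure for this endpoint. Its power figures in 19.1 (80% for 70 v 35, 78% for 35 v 35 one-sided) concern the 48-hour SOFA. They reproduce (79.7% and 77.9% by noncentral t) and are not affected.

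**Inputs**
- d0, d1: proportions dead by Day 7 on placebo and on drug. Not in the documents, so assumed. The drug is taken to halve deaths: d1 = d0/2.
- r: proportion with Day 7 SOFA above 5 among patients who survive on either treatment. Assumed 30%, borrowing the multiple organ failure rate in 9.1.
- q: the same proportion among saved patients, meaning those who would have died by Day 7 on placebo but survive on the drug. Assumed 60% to 100%.
- d0 in the ITT set: section 9.1 gives 35% mortality, with no time point, in patients needing at least four red cell units. If 30% to 75% of those deaths fall by Day 7 (assumed), d0 = 0.35 x 0.30 = 10.5% to 0.35 x 0.75 = 26.3%; 10% to 26% is used. The middle value is 0.35 x 0.50 = 17.5%.
- d0 among patients alive at 48 hours: 3% to 8% between 48 hours and Day 7 (assumed).

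**Formulas** (drug minus placebo; positive means apparent harm)
- Deaths as non-events: placebo (1 - d0)r, drug (1 - d0)r + (d0 - d1)q. Difference = (d0 - d1)q.
- Deaths excluded: placebo r, drug [(1 - d0)r + (d0 - d1)q]/(1 - d1). Difference = (d0 - d1)(q - r)/(1 - d1).
- Death as event: add d0 and d1 to the first line. Difference = -(d0 - d1)(1 - q).

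**Results** (placebo v drug, %, difference in points)

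| Set | d0 to d1 | q | Deaths as non-events | Deaths excluded | Death as event |
|---|---|---|---|---|---|
| Alive at 48 h | 3 to 1.5 | 0.6 | 29.1 v 30.0 (+0.9) | 30.0 v 30.5 (+0.5) | 32.1 v 31.5 (-0.6) |
| Alive at 48 h | 8 to 4 | 1.0 | 27.6 v 31.6 (+4.0) | 30.0 v 32.9 (+2.9) | 35.6 v 35.6 (0) |
| ITT | 10 to 5 | 0.6 | 27.0 v 30.0 (+3.0) | 30.0 v 31.6 (+1.6) | 37.0 v 35.0 (-2.0) |
| ITT | 17.5 to 8.75 | 0.6 | 24.75 v 30.0 (+5.25) | 30.0 v 32.9 (+2.9) | 42.25 v 38.75 (-3.5) |
| ITT | 17.5 to 8.75 | 1.0 | 24.75 v 33.5 (+8.75) | 30.0 v 36.7 (+6.7) | 42.25 v 42.25 (0) |
| ITT | 26 to 13 | 1.0 | 22.2 v 35.2 (+13.0) | 30.0 v 40.5 (+10.5) | 48.2 v 48.2 (0) |

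The formulas give three general results:
- With deaths as non-events, a life-saving drug looks worse whenever any saved patient has SOFA above 5.
- With deaths excluded, it looks worse only when q exceeds r. At q = r the difference is zero.
- With death as an event, it never looks worse.

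For scale, take the 17.5% row with q = 1. The standard error at 35 v 35 is sqrt[(0.2475 x 0.7525 + 0.335 x 0.665)/35] = 0.108, so 8.75 points is about 0.8 SE. The 4.0 points in the second row are about 0.37 SE (4.0/10.9).

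**The case against.** The strongest reply is that this is silence. Section 19.3 defers full analysis detail to a separate SAP, which could classify early deaths, and 19.11 might be read to cover them. That stands in part: a reader might infer that the protocol counts early deaths as successes, and it does not say so. Neither non-event nor exclusion is laid down. But the gap is in the endpoint definition, where this protocol does settle death for CTCOFR and for the 48-hour outcome. An SAP that counted deaths as cases would be changing the stated definition. A general imputation sentence that never mentions death is not a rule for it.

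The second reply concerns size, and it stands. The 35% mortality has no time point and must not be read as a Day 7 rate. Patients not expected to survive 48 hours are excluded (12.2), and deaths before 48 hours are replaced and fall outside the evaluable set. Per protocol is the main analysis for the primary outcome (19.5); the set for secondary endpoints is not stated. The larger figures therefore apply only to an ITT analysis, and even 8.75 points is less than one standard error.

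Third, mortality, CTCOFR and the 48-hour endpoint are reported alongside, so a shift in deaths should be visible elsewhere. A reader might infer that the trial's main conclusion is at risk. It is not: the endpoint is secondary, the primary analysis and its power are untouched, and 19.1 sets no phase 2b gate on it.

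Fourth, a composite has its own weakness. At q = 1 it shows 42.25% v 42.25% and hides a halving of deaths. That is a reason to show the components.

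A reader might also extend the point to mean SOFA over Days 2-5. How deaths enter that mean is a matter for the SAP, so it is not raised here.

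**Conclusion.** The point holds for this one secondary endpoint: its definition omits death, while two related endpoints in the same protocol account for it. The consequence is a possible reversal of direction, conditional on how deaths are handled and on how sick the saved patients are.

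With deaths as non-events, halved deaths and q from 0.6 to 1, the false harm is about 1-4 points among patients alive at 48 hours (3-8% dying by Day 7) and about 3-13 points in the ITT set (10-26% dead by Day 7). With deaths excluded it is smaller, and zero if saved patients resemble other survivors. The death rates, the halving, r and q are all assumptions. What does not depend on them is the direction of the error and the fact that the protocol leaves the classification open. This should be corrected, but the damage is to the interpretation of one endpoint.

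**What to change.** In 11.3.2, 11.5 and 19.6, define the event as death by Day 7 or a Day 7 SOFA above 5. State that a patient discharged alive before Day 7 is a non-case; such patients may have no Day 7 score, because 13.8.3 collects the daily laboratory values only while the patient is in hospital. Report the death and SOFA components separately, next to the mortality endpoints.

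The cost is wording only: SOFA to Day 7, hospital stay and mortality are already collected. The drawback is that a composite can mask a shift from death to organ failure, which showing the two components addresses.
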